**Handling of Participant Withdrawals or Termination:**

Although subjects may withdraw from the study at any time and for any reason, (or may be withdrawn at the investigator's discretion), subject withdrawal should be avoided as much as reasonably possible. In any case, appropriate follow-up for withdrawals or termination. Subjects who are discontinued are not to be replaced. For subjects considered discontinued, the CRF must be completed up to the last visit performed.

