	
Exclusion Criteria
 

– Change of surgical plan from elective into emergency CABG surgery

– Additional procedures other than coronary artery bypass graft procedure

– Onset of myocardial infarction within the last three months

– Blood creatinine level > 2 mg/dL

– ALT/AST level > 1.5x of normal value

– Use of preoperative intra-aortic balloon pump

– History of stroke with onset of less than 3 months

– Preoperative atrial fibrillation

– Heart conduction problem or pacemaker use

– Contraindications to pulmonary artery catheter insertion

 
Drop out criteria
 

– Stroke after surgery

– Perioperative myocardial infarction based on type 5 myocardial infarct criteria

– Haemorrhage complications requiring repeat surgery

– Use of continuous veno-venous hemofiltration or haemodialysis after coronary artery bypass graft surgery

– Delayed sternal closure

– Aortic cross-clamp duration of > 120 minutes and/or cardiopulmonary bypass duration of >180 minutes

Study Product, Dose, Route, Regimen	

– Glutamine Group: will receive intravenous infusion of 0.5 mg/kgbw L-alanyl-L-glutamine dipeptide (Dipeptiven, Fresenius Kabi, Bad Homburg, Germany) diluted in normal saline up to 500 mL, started after induction of anesthesia for 24 hours.

	

– Control Group: will receive intravenous infusion of 500 mL normal saline, started after induction of anesthesia for 24 hours

Statistical Methodology	
Primary Endpoint
 
Plasma glutamine before induction to anesthesia and 24 hours after CPB, and plasma troponin I before induction to anesthesia, 5 minutes, 6 hours, 24 hours and 48 hours after CPB.
 
Secondary Endpoint
 
Alpha-Ketoglutarate, myocardial injury score, apoptosis index, anti-cardiac troponin I expression, ejection fraction, cardiac index, plasma lactate, intensive care unit ventilation time, intensive care unit length of stay and vasoactive inotropic score.

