### **Reasons for Withdrawal or Termination:**

A subject may be discontinued from the study at any time if the subject or the investigator feels that it is not in the subject's best interest to continue. The following is a list of possible reasons the subjects will be **dropped out** from the study:

- Stroke after surgery
- Perioperative myocardial infarction based on type 5 myocardial infarct criteria
- Haemorrhage complications requiring repeat surgery
- Use of continuous veno-venous hemofiltration or haemodialysis after coronary artery bypass graft surgery
- Delayed sternal closure
- Aortic cross-clamp duration of > 120 minutes and/or cardiopulmonary bypass duration of >180 minutes

All subjects are free to withdraw from participation at any time, for any reason, specified or unspecified, and without prejudice. Reasonable attempts will be made by the investigator to provide a reason for subject withdrawals. The reason for the subject's withdrawal from the study will be specified in the subject's source documents and the Case Report Form (CRF). If a subject is withdrawn from treatment due to an adverse event, the subject will be followed and treated by the investigator until the adverse event has resolved or stabilized.

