**Methods of Intervention:**

Subjects eligible for the study will review and undergo informed consent. Once consented, subjects will be randomly assigned to undergo:

- Glutamine Group, blind: will receive intravenous infusion of 0.5 mg/kgbw L-alanyl-L-glutamine dipeptide (Dipeptiven, Fresenius Kabi, Bad Homburg, Germany) diluted in normal saline up to 500 mL, started after induction of anesthesia for 24 hours
- Control Group, blind: will receive intravenous infusion of 500 mL normal saline, started after induction of anesthesia for 24 hours

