### **SAMPLE SIZE JUSTIFICATION**

#### **Sample size calculations**

The sample size of this study is obtained from the two-way hypothesis testing formula for the two mean values in two independent groups with a confidence index ( $\alpha$ ) of 95% and power of 80%. Results are considered statistically significant if  $p < 0.05$ . The details of the estimated size of the research subject are as follows:

$$n_1 = n_2 = 2 \left[ \frac{(Z_\alpha + Z_\beta)s}{(X_1 - X_2)} \right]^2 = 2 \left[ \frac{(1.96 + 0.84) 0.04}{(0.032)} \right]^2$$

$$n_1 = n_2 = 24.5 \text{ subjects} \rightarrow 25 \text{ subjects per group}$$

Legend:

$n_1$  : Number of subjects in the intervention group (glutamine group)

$n_2$  : Number of subjects in the control group

$s$  : Standard deviation = 0.0415

$Z_\alpha$  : Z value in 95% confidence index = 1.96

$Z_\beta$  : Z value of test power = 0.84

$X_1 - X_2$  : Difference in mean value = 0.032

Assuming a 20% drop out event, the final sample size are:

$$n = 50 + (50 * 20\%)$$

$$n = 50 + 10$$

$$n = 60 \text{ subjects}$$

For a fixed sample size design, the sample size required to achieve a power of  $1-\beta=0.84$  for a two sided t-test at level  $\alpha=0.05$  under these assumptions amounts to a total of 60 patients, or 30 patients in each treatment group.

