#### Secondary Endpoint

Alpha-Ketoglutarate, myocardial injury score, apoptosis index, anti-cardiac troponin I expression, ejection fraction, cardiac index, plasma lactate, intensive care unit ventilation time, intensive care unit length of stay and vasoactive inotropic score.

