### **ASSESSMENT OF SAFETY**

Adverse events will be monitored and collected by the study team from the point of signed consent until the adverse event(s) are resolved and subjects are stabilized. For each adverse event, a detailed explanation will be obtained from the subject and subject's medical record. All adverse events will be recorded on the CRFs.

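### Five serious complications are drop-out criteria with only partial data collection afterwards and no event table by arm, so the secondary morbidity comparison could omit the worst cases, hiding either a harm or a benefit

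*Combined protocol and SAP*

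**What the plan says.** The Study Summary and Reasons for Withdrawal or Termination give the same six drop-out criteria. Five are serious clinical events: stroke, type 5 myocardial infarction, "Haemorrhage complications requiring repeat surgery", haemofiltration or haemodialysis, and delayed sternal closure. The sixth is a limit on cross-clamp or bypass time. Methods of Intervention has the infusion "started after induction of anesthesia for 24 hours", so treatment is already running when these events can arise.

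On data after drop-out, Handling of Participant Withdrawals or Termination says "For subjects considered discontinued, the CRF must be completed up to the last visit performed". The same section mentions appropriate follow-up in an unfinished sentence and rules out replacement. Reasons for Withdrawal or Termination puts the reason on the CRF. For a patient withdrawn from treatment because of an adverse event, it adds that "the subject will be followed and treated by the investigator until the adverse event has resolved or stabilized". Assessment of Safety says "All adverse events will be recorded on the CRFs". The CRF page Research Sample Outcomes has a Yes/No row for each of the five events, as well as for death and other complications.

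Goal 4 of the study is lower postoperative morbidity, judged by ventilator time, ICU time and vasoactive or inotrope use. The Secondary Endpoint list includes "ejection fraction, cardiac index, plasma lactate, intensive care unit ventilation time, intensive care unit length of stay and vasoactive inotropic score". The Statistical Analysis Plan covers randomisation, sample size, endpoints and safety recording. It names no analysis population, no handling of drop-outs and no comparison of events by arm. Sample size calculations adds patients under the heading "Assuming a 20% drop out event, the final sample size are".

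**The concern.** Whether a patient has one of the five events is known only after treatment begins, and treatment may affect it. Type 5 infarction is itself a form of the myocardial damage that glutamine is meant to reduce. Patients with these events are also likely to have long ICU and ventilator times.

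If they are removed, ICU time, ventilator time and vasoactive-inotropic score (VIS) are compared only among patients who avoided the worst complications. An excess of events on glutamine would not show in those endpoints, and neither would a reduction. No planned event table would reveal the imbalance.

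The plan also has no rule for a patient who dies before extubation or ICU discharge, the points at which the two durations end. At stake is the morbidity conclusion. The primary endpoints, plasma glutamine and troponin I, are not the subject of this point.

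**Working it through.** **1. The plan's own figure.** Sample size calculations uses SD 0.04, difference 0.032, and Z values 1.96 and 0.84:

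n = 2 × [(1.96 + 0.84) × 0.04 / 0.032]² = 24.5, rounded to 25 per group, or 50 in total.

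Adding 20% of 50 gives 10 more, so 60 in total and 30 per arm. This reproduces. Ten is a planning allowance, not a cap: 20% of 60 would be 12. How many drop-outs would be clinical events is not stated.

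**2. What is captured after one of the five events.**

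| Item | Source | Position |
|---|---|---|
| The event | CRF outcomes page; withdrawal reason; adverse event record | Recorded |
| Course of the adverse event | Reasons for Withdrawal; Assessment of Safety | Followed until resolved or stabilised |
| ICU time, ventilator time, vasoactive doses | Data Collection (from the medical record); CRF | Retrievable, but required only up to the last visit |
| Summary of events by arm | None | Not planned |
| Inclusion in the morbidity analysis | None | Not stated |

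**3. Size of an event imbalance (illustrative counts, 30 per arm).** The risk difference is glutamine minus control, D = a/30 - b/30, with a 95% Newcombe interval. From the Wilson limits (l, u) of each arm, the lower bound is D - √[(p₁ - l₁)² + (u₂ - p₂)²] and the upper bound is D + √[(u₁ - p₁)² + (p₂ - l₂)²].

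| Events, glutamine v control | D | 95% interval |
|---|---|---|
| 0 v 0 | 0.000 | -0.114 to 0.114 |
| 3 v 1 | 0.067 | -0.082 to 0.225 |
| 7 v 3 | 0.133 | -0.061 to 0.321 |
| 10 v 0 | 0.333 | 0.152 to 0.512 |

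Opposite splits reverse the signs: 3 v 7 gives -0.133 (-0.321 to 0.061).

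**4. Effect on the ICU comparison.** Let P be the chance that a random glutamine patient stays longer in ICU than a random control patient, with ties counted as half. Assume that event patients stay longer than all others, and that patients are otherwise alike between arms. With event proportions p₁ (glutamine) and p₀ (control):

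P = p₁(1 - p₀) + ½[p₁p₀ + (1 - p₁)(1 - p₀)] = 0.5 + 0.5 × (p₁ - p₀).

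- 3 v 1: 0.5 + 0.5 × 0.067 = 0.53
- 7 v 3: 0.5 + 0.5 × 0.133 = 0.57
- 10 v 0: 0.5 + 0.5 × 0.333 = 0.67
- 3 v 7: 0.5 - 0.5 × 0.133 = 0.43

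If event patients are dropped, P = 0.50 in every case. If they are kept but stay no longer than the others, it is also 0.50. For a given split, P therefore lies between 0.50 and the value shown.

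**The case against.** The strongest reply is that little is actually lost. The events have their own CRF rows beside death and sepsis, so the form seems to expect completion for dropped patients. Adverse events are followed to resolution. ICU time, ventilator time and vasoactive use come from the medical record of a single hospital stay, so the last-visit rule may be template wording. The 20% allowance could equally cover missing plasma samples. Blinding protects decisions to drop a patient.

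Much of this stands. A reader might infer that the complications go unrecorded, or that the plan excludes these patients from analysis. The documents contradict the first and do not state the second. A reader might also take the ten allowed drop-outs as a ceiling, or assume that the bias favours glutamine. Neither is supported.

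Two things remain. Data that can be retrieved are not data that must be collected, and clinical follow-up of an adverse event does not mention endpoint data. Blinding, for its part, does not remove selection on an outcome that treatment may affect.

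It is also fair to say that keeping these patients would seldom change a significance test in the milder cases. With event patients ranked highest, a rank-sum test rejects in about 5% of simulated trials at 3 v 1 and 8% at 7 v 3. That limits the practical effect there, but it does not justify a comparison restricted to uncomplicated patients.

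**Conclusion.** The point holds in conditional form. The plan drops patients for five serious events that can follow the start of treatment, requires their CRF only to the last visit, plans no event summary by arm, and does not say whether they count in the morbidity endpoints. If they do not count, those endpoints could hide a harm or a benefit.

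In the illustrations, the hidden risk difference runs from 7 points (3 v 1) to 33 points (10 v 0), in either direction. The ICU measure would move from 0.50 to as much as 0.53 and 0.67 respectively. These figures are not bounds. They rest on assumed event counts, 30 per arm, and event patients having the longest stays. The direction of bias is unknown.

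This should be corrected, but it does not undermine the trial: the affected endpoints are secondary. Confidence is medium, because exclusion from analysis is inferred and not stated.

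**What to change.** 1. **Data collection.** Amend both withdrawal sections so that these events stop study treatment only if clinically needed and never stop data collection. For every randomised patient who started the infusion, complete the CRF durations page, the outcomes page and the vasoactive doses for the first 24 h in ICU from the medical record, to hospital discharge or death. The exception is a patient who withdraws consent to data use. Add a hospital-discharge date to the CRF timeline. Allocation is blinded, so failure to start the infusion should not depend on arm.
2. **Event table.** Add to Assessment of Safety one descriptive table of the eleven clinical events on the outcomes page, by arm, with counts, risk difference and 95% interval, and no p-values.
3. **Morbidity analysis.** Analyse ICU time, ventilator time and VIS in this population by randomised arm with a rank-based comparison. Death before ICU discharge takes the worst rank for ICU time, death before extubation the worst rank for ventilator time, and death within the first 24 h in ICU the worst rank for VIS, so that an early death cannot score favourably. Count re-intubation time in ventilator time.

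**Cost.** The Institutional Review Board section requires approval of any amendment. Chart follow-up is needed for the dropped patients, about 10 on the plan's allowance, but no extra patients. Durations will be more spread out with complicated cases included, and a rank test gives no difference in mean hours. Event intervals will be wide: even 0 v 0 leaves ±11 points.

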**Methods of Intervention:**

Subjects eligible for the study will review and undergo informed consent. Once consented, subjects will be randomly assigned to undergo:

- Glutamine Group, blind: will receive intravenous infusion of 0.5 mg/kgbw L-alanyl-L-glutamine dipeptide (Dipeptiven, Fresenius Kabi, Bad Homburg, Germany) diluted in normal saline up to 500 mL, started after induction of anesthesia for 24 hours
- Control Group, blind: will receive intravenous infusion of 500 mL normal saline, started after induction of anesthesia for 24 hours

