## STUDY SUMMARY

Title	Myocardial Protecting Role of Glutamine in Patients with Low Ejection Fraction Undergoing Elective On-Pump Coronary Artery Bypass Graft Surgery
Methodology	Randomized, double blinded, controlled study
Study Duration	Estimated duration for the main protocol (e.g. from start of screening to last subject processed and finishing the study) is approximately 1 year
Study Center	National Cardiovascular Center Harapan Kita, West Jakarta, Jakarta, Indonesia
Objectives	
Primary Objective: To determine whether intravenous glutamine could mitigate the negative impact of on-pump CABG procedures and provide better clinical outcome in patients undergoing coronary artery bypass graft surgery under cardiopulmonary bypass.
 
Secondary Objective: To determine whether intravenous glutamine could prevent the decline of plasma glutamine level, reduce myocardial damage, improve hemodynamic profile, and reduce morbidity low ejection fraction patients undergoing coronary artery bypass graft surgery under cardiopulmonary bypass.

Number of Subjects	60 randomized patients divided into two groups; Glutamine and Control
Diagnosis and Main Inclusion Criteria	
Inclusion Criteria
 

– Male and female patients, aged <math>\geq</math> 18 years old with coronary heart disease indicated for elective coronary artery bypass grafting under cardiopulmonary bypass

– Left ventricle ejection fraction of 31-50%, confirmed by echocardiography or radionuclide imaging

– No history of heart surgery

– Agree to participate in the study and signed a written informed consent

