### **Goals of the study:**

To analyze the effect of intravenous glutamine in low EF patients undergoing on-pump CABG surgery in:

1. Reducing myocardial damage by a decrease of myocardial injury score, apoptotic index and increase of anti-cardiac troponin I expression through right atrial appendage tissue sample, as well as decrease of troponin I level.
2. Improving myocardial metabolism by a decrease in plasma lactate levels, increase of plasma glutamine levels and alpha ketoglutarate ( $\alpha$ -KG) levels in the right atrial appendage tissue sample.
3. Improving hemodynamic profile through an increase in EF and cardiac index after CPB
4. Reducing postoperative morbidity by the decrease of ventilator duration, duration of intensive care, and use of postoperative vasoactive and inotropes

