## **STATISTICAL ANALYSIS PLAN**

### **RANDOMIZATION**

Subjects who meet all inclusion and exclusion criteria will be randomized into two groups, glutamine and control group. Subject allocation will be carried out through block randomization and known only by the pharmacist, and the confidentiality are maintained so that subjects, doctors/nurses, researchers, and data analysers does not know the allocation of each subject.

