#### Primary Endpoint

Plasma glutamine before induction to anesthesia and 24 hours after CPB, and plasma troponin I before induction to anesthesia, 5 minutes, 6 hours, 24 hours and 48 hours after CPB.

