## **INSTITUTIONAL REVIEW BOARD**

The protocol, informed consent form(s), and all participant materials will be submitted to the Ethics Committee for review and approval. Approval of both the protocol and consent form must be obtained before any participant is enrolled. Any amendment to the protocol will require review and approval before the changes are implemented to the study.

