**Research CRF Checklist**

Sample characteristics	
Preoperative laboratory parameters	
Surgical procedure, aortic cross-clamp and CPB	
Intervention liquid bottle number: _____	
Right atrial appendage tissue biopsy	

• a-KG level

• Myocardial injury score

• Apoptotic index

• Anti-cardiac troponin I expression

	
Plasma glutamine levels	
Troponin I levels	
Lactate levels	
Ejection Fraction	
Cardiac Index	
Post-operative vasoactive and inotropes	
Surgery duration, aortic cross-clamp duration, ICU care duration and ventilator usage duration	
Research sample outcomes	

Researcher: \_\_\_\_\_ Date: \_\_\_\_\_ Signature: \_\_\_\_\_

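### The stated glutamine dose, 0.5 mg/kg over 24 hours (35 mg for an assumed 70 kg patient), is implausibly small for the trial's aims; mass unit and time basis must be verified

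*Combined protocol and SAP*

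**What the plan says.** The experimental treatment is specified in two places, Methods of Intervention and the Study Product row of the Study Summary, and they agree. The active group "will receive intravenous infusion of 0.5 mg/kgbw L-alanyl-L-glutamine dipeptide", which is "diluted in normal saline up to 500 mL, started after induction of anesthesia for 24 hours". Neither place gives an hourly or per-minute rate, a total amount, a product concentration or a reason for the dose. No other dose appears in the text available for review.

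The effect expected of this infusion is stated several times. The objectives in the Study Summary, and again the Purpose section, ask whether "intravenous glutamine could prevent the decline of plasma glutamine level". Goals of the study looks for an "increase of plasma glutamine levels and alpha ketoglutarate" in atrial tissue. The Primary Endpoint section begins with "Plasma glutamine before induction to anesthesia and 24 hours after CPB".

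**The concern.** A dose of 0.5 mg/kg spread over a full day is tens of milligrams of dipeptide. That is very little for an infusion meant to hold up or raise the plasma concentration of an amino acid the body already carries. The likely explanations are a wrong mass unit, or a rate unit that was dropped so that only the amount per kg remains.

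This figure is the only definition of the experimental arm. If bags are prepared as written, the active arm is close to saline in glutamine content, and the trial cannot plausibly test its own hypothesis. If bags are prepared to some other reading, patients receive an intravenous exposure that the protocol does not state. That matters for safety and ethics review, and it means nobody could reproduce the treatment from the protocol.

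**Working it through.** The plan gives no derivation of the dose, so there is no figure of its own to reproduce. The check asks what the written dose amounts to and how far it could move plasma glutamine.

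**Inputs from the documents:** 0.5 mg/kg, 500 mL, 24 hours.

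**Assumptions, not in the documents:** body weight 70 kg (range 50 to 90); dipeptide molar mass 217.2 g/mol, giving one glutamine per molecule; distribution volume V of 0.045 L/kg (plasma only) to 0.2 L/kg (extracellular fluid); half-life 0.5 to 8 h; endogenous plasma glutamine 300 to 800 micromol/L.

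**1. Total dose.** 0.5 mg/kg × 70 kg = 35 mg (25 mg at 50 kg, 45 mg at 90 kg). The bag holds 35 mg / 500 mL = 0.07 mg/mL, delivered at 35 mg / 24 h = 1.46 mg/h.

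**2. Glutamine supplied.** 0.5 mg/kg ÷ 217.2 g/mol = 2.30 micromol/kg, or 2.30 / 24 = 0.0959 micromol/kg/h.

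**3. Ceiling with no clearance** (dose per kg ÷ V; body weight cancels):
- V = 0.2 L/kg: 2.302 / 0.2 = 11.5 micromol/L. This is 11.5/800 = 1.4% to 11.5/300 = 3.8% of the endogenous level.
- V = 0.045 L/kg: 2.302 / 0.045 = 51.2 micromol/L, or 6.4% to 17%. This requires every molecule to stay in plasma for 24 hours, which is unrealistic.

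**4. Rise at end of infusion with clearance.** Rise = rate / (k × V) × (1 − exp(−24k)), with k = ln 2 / half-life. Results in micromol/L:

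| Half-life (h) | V = 0.045 L/kg | V = 0.2 L/kg |
|---|---|---|
| 0.5 | 1.54 | 0.35 |
| 1 | 3.07 | 0.69 |
| 2 | 6.15 | 1.38 |
| 4 | 12.1 | 2.72 |
| 8 | 21.5 | 4.84 |

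The range is 0.35/800 = 0.04% to 21.5/300 = 7.2% of the endogenous level.

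**5. A second check, by turnover.** Against an assumed endogenous turnover of 100 to 400 micromol/kg/h, the infusion adds 0.0959/400 = 0.02% to 0.0959/100 = 0.10%.

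**6. Other readings of the same statement, for 70 kg over 24 hours:**

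| Reading | Total dipeptide |
|---|---|
| As written | 35 mg |
| Per hour: 0.5 × 70 × 24 | 840 mg |
| Grams per kg: 0.5 × 70 | 35 g |
| Per minute: 0.5 × 70 × 1,440 | 50.4 g |

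The largest is 50,400 / 35 = 1,440 times the smallest. On the per-hour reading the rises in step 4 are multiplied by 24, giving about 8 to 517 micromol/L.

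**The case against.** Several points on the other side have force.

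- **The inference needs outside inputs.** Volume, half-life and endogenous level are all assumed, and the documents do not give the size of the fall to be prevented. The rise can only be compared with an assumed total level. That is true, and it makes the conclusion a judgement of plausibility. But the step 3 ceilings do not depend on half-life, and the realistic one is under 4% of the assumed level.
- **Nothing in the documents contradicts the dose.** The two statements agree, and amount, volume and duration together read as a complete total dose. This stands: it is not an internal inconsistency. A dose written as intended but badly chosen is not excluded either, though it would serve the stated aims no better.
- **The missing-rate explanation is weaker than the wrong-unit one.** No section hints at a dropped rate. The 517 micromol/L on the per-hour reading needs the plasma-only volume with an 8-hour half-life; at 0.2 L/kg the top is 4.84 × 24 = 116 micromol/L. By turnover, 840 mg adds only about 0.6% to 2.3%. The per-minute reading does reach gram scale. This limits what can be said about which correction is right, and is the reason to verify both parts.
- **The end of infusion is not the endpoint time.** The infusion starts after induction and lasts 24 hours, while the sample is drawn 24 hours after bypass, so an infusion run as written has stopped by then. This is correct, but it makes the rise smaller. With an assumed 3-hour gap and a 0.5-hour half-life it falls a further 2^6 = 64-fold.

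**Conclusion.** The concern holds. As written, the dose is 35 mg over 24 hours for an assumed 70 kg, and the resulting rise in plasma glutamine is at most about 22 micromol/L at the end of infusion under the assumed volumes and half-lives. Against an assumed 300 to 800 micromol/L, that cannot plausibly serve the plasma glutamine aims or the glutamine part of the primary endpoint. The statement is very probably wrong in its mass unit or in a missing time basis. The documents do not settle which, and this review does not say what the right figure is. Because it is the sole specification of the experimental treatment, it must be corrected.

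**What to change.** Check both the mass unit and the time basis against the product labelling and the pharmacy preparation records. Correct the dose in Methods of Intervention and in the Study Summary to the verified figure. A useful optional addition is a worked example for one body weight: total dose, mL of product, final bag concentration and mL/h.

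If patients have already been treated, establish what they received. The CRF records body weight and, in the checklist, the "Intervention liquid bottle number"; these can be linked to the preparation records. The allocation is "known only by the pharmacist", so the pharmacist should do the linking to keep the blind. A dose field on the CRF is best avoided, since it could reveal allocation to staff.

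The cost is a short amendment to two places and a check of pharmacy records. The Institutional Review Board section applies: "Any amendment to the protocol will require review and approval before the changes are implemented to the study". If the bags were made to the intended dose, only the text changes. If they were made as written, patients already treated had a different exposure, and how they are analysed must be decided and reported.
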